4.3.6. Safety Analysis Set

The Safety analysis set includes all randomized patients who actually received at least 1 dose or partial dose of the IMP, analyzed according to the treatment actually received.

Randomized patients for whom it is unclear whether the study medication was taken will be included in the safety analysis set as randomized.

For patients receiving more than one IMP (placebo and dupilumab) during the study, the actual treatment group for as treated analysis will be the dupilumab group.

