Polysomnography (PSG) sub-study: Of the 201 participants, approximately 30 patients total (approximately 20 dupilumab and 10 placebo patients) will participate in a PSG sub-study at selected US sites. Each patient who participates in this sub-study will have a total of 3 overnight PSGs: at baseline, 2 (preferably) consecutive overnight PSGs to control for “first night effect” (night of Day -2) and collect baseline data (night of Day -1; which will serve as baseline assessments); then 1 overnight PSG at week 12. The assessment procedure is provided in [Section 10.10](#).

Study interventions

Investigational medicinal products

- Formulation:
 - Dupilumab: 150 mg/mL in pre-filled syringe to deliver 300 mg in 2 mL,
 - Placebo: Pre-filled syringe to deliver 2 mL of vehicle solution, containing all ingredients except the protein (dupilumab), visually indistinguishable from the dupilumab syringe.
- Route of administration: Subcutaneous
- Dose regimen:
 - Patients initially assigned to dupilumab will receive 600 mg (2 x 300 mg dupilumab injections) on Day 1 (ie, the loading dose), followed by 1 dupilumab injection of 300 mg every 2 weeks (Q2W) until week 10, then 1 dupilumab +1 placebo injection at week 12 (to protect the blind while placebo patients receive their loading dose), followed by 1 dupilumab injection Q2W, with a last injection at week 22.
 - Placebo patients will receive 2 x 2 mL placebo injections on Day 1, then 1 placebo injection Q2W until week 10, and then 2 x 300 mg dupilumab injections at week 12 (ie, the loading dose), followed by 1 dupilumab injection Q2W, with a last injection at week 22.

Post-trial access to study medication

After the study is completed, patients will not be provided any further study medication as part of this protocol.

Statistical considerations:

- **Primary analysis:**

The percent change from baseline to week 12 in sleep quality NRS will be analyzed using a mixed effect model with repeated measures (MMRM) with treatment, baseline value, randomization stratum, visit, treatment by visit interaction, and baseline value by visit interaction terms (all as fixed effects) in the model.

- **Analysis of secondary endpoints:**

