9.4.2 Safety analyses

All safety analyses will be performed on the Safety Population.

Table 5 - Safety analyses

Endpoint	Statistical Analysis Methods
AE, SAE, AE leading to death, AE leading to permanent treatment discontinuation	Treatment emergent adverse event (TEAE) incidence tables will be presented by system organ class (SOC), high-level group term (HLGT), high-level term (HLT) and preferred term (PT) for each treatment group and overall, showing the number (n) and percentage (%) of patients experiencing a TEAE. Multiple occurrences of the same event in the same patient will be counted only once in the tables. The denominator for computation of percentages is the safety population within each treatment group. In addition, TEAEs will be described according to maximum intensity and relation to the study drug. AEs that occur outside the treatment emergent period will be summarized separately. Proportion of patients with at least 1 TEAE, treatment emergent SAE, TEAE leading to death, and TEAE leading to permanent treatment discontinuation will be tabulated by treatment group and overall. All Tables will be provided separately for the double-blind treatment period, and for the entire study.

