This document provides the detailed statistical methodology for the analysis of data from the Sanofi Group study LPS15497. The table, listing and figure shells supporting the statistical analysis plan (SAP) can be found in a separate SAP shell document.

The analyses described herein are based on the clinical trial protocol (Amendment 2), Version 1.0, dated on 7th April 2020. Any changes or revisions to the planned analysis described in this document will be made prior to database lock.

2. Study Objectives, Endpoints and Estimands

The study objectives and corresponding endpoints are shown in the [Table 3.1.1](#).

Table 3.1.1- Objectives and endpoints

Objectives	Endpoints
Primary	

 To evaluate the effect of dupilumab on sleep quality in adult patients with moderate to severe atopic dermatitis (AD) 	
 Percentage change from baseline to week 12 in sleep quality numerical rating scale (NRS)
Secondary	

 To evaluate the effect of dupilumab on objective and subjective quantitative sleep parameters, AD-related outcomes, and the daytime 	
 Change from baseline to week 12 in sleep efficiency (SE) based on actigraphy data Change from baseline to week 12 in total sleep time (TST) based on actigraphy data Change from baseline to week 12 in wake after sleep onset (WASO) based on actigraphy data

consequences of sleep deprivation

- Change from baseline to week 12 in sleep onset latency (SOL) based on actigraphy data
- Percent change from baseline to week 12 in Pruritus NRS
- Change from baseline to week 12 in SCORing Atopic Dermatitis (SCORAD) total score
- Change from baseline to week 12 in SCORAD sleep Visual Analog Scale (VAS)
- EASI50 (reduction of Eczema Area Severity Index [EASI] score by $\geq 50\%$ from baseline) at week 12
- EASI75 (reduction of EASI score by $\geq 75\%$ from baseline) at week 12
- EASI90 (reduction of EASI score by $\geq 90\%$ from baseline) at week 12.
- Change from baseline to week 12 in Patient Oriented Eczema Measure (POEM) total score
- Change from baseline to week 12 in Dermatology Life Quality Index (DLQI) total score
- Change from baseline to week 12 in Patient-Reported Outcomes Measurement Information System (PROMIS) Sleep Related Impairment SF8a Total Score

- To continue to assess safety and tolerability of dupilumab throughout the study

- Incidence of adverse events through week 12

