3.1. Overall Study Design and Plan

This is a Phase IV, prospective, 2:1 randomized, multinational, multicenter study, with a 12-week double-blind placebo-controlled period, followed by a 12-week open label extension to evaluate the effect of dupilumab on sleep in adult patients with moderate to severe AD.

[figure not shown]
Approximately 201 participants will be randomly assigned to study intervention in a 2:1 dupilumab to placebo ratio from multiple sites globally such that at least 150 evaluable participants (100 in the active group and 50 in placebo) complete the double-blind portion (to week 12) of the study.

The study will comprise of:

- Screening Period 1 (Day -28 to -8): Patients will be evaluated according to inclusion and exclusion criteria
- Screening Period 2 (Day -7 to -1; pre-baseline assessments): eligible patients will complete the daily sleep quality, daily pruritus, skin pain, skin sensitivity, and touch skin burn, sleep diary, and will wear an actigraph at night-time during the 7 days immediately preceding the Baseline visit (Day 1). If preferred by the patient and the investigator for logistical reasons, screening can be done during a single on-site visit. In that case, all procedures planned at screening 1 and screening 2 should be done during this single screening visit. Importantly, this single screening visit will have to be done at least 7 days before the baseline visit, as patients should wear the actigraph and complete the diary for 7 days before baseline.
- Baseline (Day 1): Patients who remain eligible will be randomized
- 12-week double-blind placebo-controlled period: Patients will be randomized to receive dupilumab or placebo
- 12-week open-label extension period: following completion of double-blind period, patients randomized to dupilumab will continue to receive active treatment for open-label period, whereas patients randomized to placebo will receive active treatment with dupilumab.

The maximum study duration per participant will be 28 weeks. A patient is considered to have complete the study if he/she has completed all phases of the study including the last scheduled visit shown in the Schedules of Activities (see [Appendix 15.2](#)).

Figure 3-1 Study Plan

Abbreviations: q2w=every 2 weeks

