8.2.23. Multiplicity issues

The overall type-I error rate will be controlled at the two-sided 0.05 level using a sequential testing procedure. In order for any secondary endpoints to be eligible for being declared significant, the primary endpoint must be significant at 0.05 significance level. The secondary endpoints will be tested following the hierarchical testing procedure with a pre-specified order, that is, inferential conclusions about successive secondary endpoints require statistical significance at 0.05 significance level of the previous one.

The following key secondary endpoints will be included in the multiplicity adjustment scheme and tested in the following order:

1. Percent change from baseline to Week 12 in peak pruritus NRS
2. Change from baseline to Week 12 in SCORAD total score
3. Change from baseline to Week 12 in SCORAD sleep VAS
4. Change from baseline to Week 12 in PROMIS Sleep Impairment SF8a score
5. Change from baseline to Week 12 in TST based on actigraphy data
6. Change from baseline to Week 12 in SE based on actigraphy data
7. Change from baseline to Week 12 in WASO based on actigraphy data
8. Change from baseline to Week 12 in SOL based on actigraphy data

Each endpoint will be tested at 0.05 (two-sided) level of significance. If at any step the null statistical hypothesis of no treatment difference is not rejected, the endpoints listed after that step will be reported at nominal level, otherwise will be technically eligible for being declared significant. Regardless of eligibility for being declared significant, all endpoints (non-key secondary and exploratory) will be tested at 0.05 (two-sided) level of significance and reported at nominal level.

9. Safety Analysis

All safety results will be summarized separately within the double-blind treatment period and the overall period (combined double-blind and OLE periods), using the Safety analysis set by actual treatment group and overall.

The observation periods include:

- The **pre-treatment** period is defined as the time from the signed informed consent date up to first administration of the IMP.
- The **randomized on-treatment** period is defined as the time from the first administration of the IMP (on Day 1) to the last administration of the IMP prior to Week 12 + 14 days if the patient does

not enter the OLE period, or until prior to the loading dose at Week 12 if the patient enters the OLE period.

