9.1. Adverse Events

The adverse event observation periods include:

- **Pre-treatment adverse events** are adverse events that developed or worsened or became serious from the signed informed consent date up to the first administration of the IMP.
- **Treatment-emergent adverse events** are adverse events that developed or worsened or became serious during the TEAE period.
- **Post-treatment adverse events** are adverse events that developed or worsened or became serious after TEAE period.

The primary focus of adverse event reporting will be on treatment-emergent adverse events. Pre-treatment and post-treatment adverse events will be summarized separately.

All adverse events will be coded to a LLT, PT, HLT, HLGT, and associated primary SOC using the version of Medical Dictionary for Regulatory Activities (MedDRA) currently in effect at Sanofi at the time of each database lock.

Adverse events will be recorded from the time of signed informed consent until the end of the study or the resolution/stabilization of all SAE and AESI.

If an adverse event date/time of onset (occurrence, worsening, or becoming serious) is incomplete, an imputation algorithm will be used to classify the adverse event as pre-treatment, treatment-emergent, or post-treatment. The algorithm for imputing date/time of onset will be conservative and will classify an adverse event as treatment-emergent unless there is definitive information to determine it is pre-treatment or post-treatment. Details on classification of adverse events with missing or partial onset dates are provided in [Section 15.4.4](#).

Adverse event will be summarized by primary SOC, HLGT, HLT, and PT, sorted in alphabetical order for each treatment group using number and percentage of patients experiencing an adverse event. Multiple occurrences of the same event in the same patient will be counted only once in the tables within a treatment phase. The denominator for computation of percentages is the safety analysis set within each treatment group.

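### The as-treated rule puts placebo patients who later receive open-label dupilumab into the dupilumab column of the Week 12 safety tables

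*SAP*

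**What the plan says.** - **The grouping rule.** SAP section 4.3.6 analyses the safety set by treatment actually received. It then adds that for anyone given "more than one IMP (placebo and dupilumab) during the study, the actual treatment group for as treated analysis will be the dupilumab group". The scope is the whole study.
- **The design.** SAP section 3.1 describes the open-label period, in which dupilumab patients continue, "whereas patients randomized to placebo will receive active treatment with dupilumab". The protocol synopsis gives the placebo arm "2 x 300 mg dupilumab injections at week 12 (ie, the loading dose), followed by 1 dupilumab injection Q2W".
- **Where the grouping is used.** SAP section 9 opens: "All safety results will be summarized separately within the double-blind treatment period and the overall period", and this is done "using the Safety analysis set by actual treatment group and overall". SAP section 9.1 adds: "The denominator for computation of percentages is the safety analysis set within each treatment group". SAP section 7.2 groups exposure and compliance by actual treatment group too. The AESI and vital sign summaries (sections 9.1.7 and 9.3) use the same set by treatment group.
- **The endpoint affected.** SAP Table 3.1.1 lists "Incidence of adverse events through week 12" as a secondary endpoint. Protocol section 9.4.2 requires that "All Tables will be provided separately for the double-blind treatment period, and for the entire study".

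**The concern.** A rule of this kind is usually aimed at dispensing errors, where a placebo patient is given an active kit by mistake. Here it is not limited to errors or to the double-blind period. Receiving both products is the planned course for every placebo patient who continues at Week 12, so the rule catches the bulk of the placebo arm.

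Two things follow for the double-blind tables. Events that occurred while a patient was on placebo are counted under dupilumab. The patients left under placebo are almost only those who did not receive open-label dupilumab, a group selected by dropout, tolerability and lack of effect. The comparison is then no longer between randomized groups, and its bias can go in either direction depending on the event.

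The double-blind period is the only placebo-controlled part of this trial, so it is the only source of a controlled adverse event comparison.

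**Working it through.** **1. Arm sizes.** The plan states 100 dupilumab and 50 placebo evaluable patients for 90% power, with a difference of 25, SD 44 and two-sided alpha 0.05.
- Placebo n = (1.960 + 1.282)² × 44² × (1 + 1/2) / 25² = 48.8, so 49, and the total is 3 × 49 = 147 against 150 stated.
- With 50 and 100, power is 0.907. The stated figure reproduces and is not in dispute.
- About 201 randomized at 2:1 gives 134 dupilumab and 67 placebo. If all are dosed as randomized, these are the safety columns one would expect.

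**2. Does the rule reach the double-blind tables?**
- Section 4.3.6 fixes one actual treatment group per patient from everything received during the study.
- Section 9 uses that group for both reporting periods.
- The period definitions in section 9 end the randomized on-treatment period before the Week 12 loading dose for patients entering the extension. That decides which events are counted, not which column the patient is in.
- Table 4.4.1 has no label for placebo followed by dupilumab.
- Section 12 locks the double-blind data after all patients complete 12 weeks. By then, placebo patients who continue will generally have had the Week 12 dose.
- Section 13 does not list the rule as a change from the protocol. Protocol section 9.3 has no rule for patients who receive both products.

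So the rule reaches them. Dupilumab patients also receive a placebo syringe at Week 12, so the wording formally covers them too, but their group does not change.

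**3. Column sizes as written.** Assume all placebo completers receive the Week 12 dupilumab dose; the documents give no extension entry rate. With dropout d, about 67 × (1 − d) placebo patients move.

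| Scenario | Moved | Placebo column | Dupilumab column | Share of dupilumab column on placebo through Week 12 |
|---|---|---|---|---|
| 10% dropout | 60 | 7 | 194 | 31% |
| 20% dropout (SAP section 4.1) | 54 | 13 | 188 | 29% |
| 50 placebo completers (SAP section 3.1) | 50 | 17 | 184 | 27% |
| 30% dropout | 47 | 20 | 181 | 26% |
| No dropout | 67 | 0 | 201 | 33% |

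**4. Dilution without selection.** Suppose the 13 remaining placebo patients had the same event rate as the whole placebo arm. The displayed risk difference is then the true one times 134/188 = 0.71. With assumed rates of 10% on placebo and 20% on dupilumab:
- Dupilumab column: (134 × 0.20 + 54 × 0.10) / 188 = 32.2/188 = 17.1%.
- Risk difference: 7.1 points instead of 10.0.
- 95% CI half-width, correct grouping: 1.96 × √(0.10 × 0.90/67 + 0.20 × 0.80/134) = 9.9 points.
- 95% CI half-width, as written: 1.96 × √(0.10 × 0.90/13 + 0.171 × 0.829/188) = 17.2 points.

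For a rarer event, at an assumed 10% on dupilumab and 2% on placebo, the dupilumab column shows (134 × 0.10 + 54 × 0.02) / 188 = 7.7%.

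**5. Selection.** Suppose 4.5% in each arm stop for an adverse event (6/134 and 3/67, assumed) and do not enter the extension. Their three placebo events stay in the small column. The table shows 6/188 = 3.2% on dupilumab against 3/13 = 23% on placebo, although the true rates are equal.

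**6. Exposure.** SAP section 7.2.1 counts duration from the first administration of either product. In the overall-period table, the 54 moved patients would add 54 × 12 = 648 patient-weeks of placebo time to dupilumab exposure.

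**The case against.** The strongest reply is that a sensible reading exists. Section 4.3.6 starts from treatment actually received, and section 9 reports each period separately and ends the double-blind period before the Week 12 loading dose. Table 4.4.1 keeps a placebo column that the literal reading nearly empties. For Week 24 efficacy the SAP groups patients by original randomization (sections 8.2.1 and 15.1), so its authors had the crossover in view. The table shells are in a separate document and may set the columns correctly. On this view the text is loose rather than wrong.

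That reading is probably what was intended, but the SAP does not state it. The period definitions select events, not groups, and shells that cannot be seen cannot be assumed to override an explicit rule. Double programming (section 4.4) checks against the same specification, so it would not catch the problem.

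Several narrower points stand:
- The trigger is a dose of dupilumab, not extension entry alone.
- A few placebo patients remain unless there is no dropout.
- No hypothesis test is planned for safety, so type I error and the efficacy conclusions are untouched.
- The event rates are illustrations, and 3/13 is an extreme case for one type of table.
- Section 9 already defines the split at the Week 12 loading dose, so part of the remedy exists.
- The existing rule also covers a dupilumab patient given a placebo kit in error. A replacement must keep that.

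**Conclusion.** The concern holds. As written, the SAP would report a secondary endpoint in the wrong columns: about 188 against 13 patients instead of 134 against 67. Roughly 29% of the dupilumab column would have had only placebo in the period being summarized. The placebo remainder is 7 to 20 patients for dropout of 10% to 30%, and they are selected on not continuing.

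The column sizes rest on the planned 2:1 split of 201, the SAP's dropout figure, and the assumption that placebo completers are dosed at Week 12. A lower extension entry rate would leave more placebo patients behind but would not remove the misclassification or the selection. The damage is to descriptive incidence, AESI, vital sign and exposure tables. It is an error in a stated rule rather than missing detail, and it should be corrected before database lock.

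**What to change.** Amend SAP section 4.3.6 so that the grouping depends on the period:

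- **Double-blind summaries.** Actual treatment is the product received from Day 1 until before the Week 12 dose. Any patient, in either arm, who received both products in that interval is analysed as dupilumab. This keeps the rule for dosing errors.
- **Overall-period summaries.** Use two sequence columns, placebo then dupilumab and dupilumab throughout. Within them, show events before and after the first open-label dose separately, using the on-treatment periods already defined in section 9. This matches the handling of Week 24 efficacy in section 15.1.
- **Labels.** Add the two sequences to Table 4.4.1. Apply the same grouping to exposure and compliance (section 7.2), adverse events including AESIs (section 9.1) and vital signs (section 9.3).

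The cost is SAP wording and table shells, with one extra column in the overall-period tables. No new data are needed and the efficacy analyses do not change.

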4.3.7. Analysis set without trial impact (disruption) due to COVID-19

The analysis set without trial impact (disruption) due to COVID-19 includes any patient:

- without any critical or major protocol deviation related to COVID-19
- and who did not permanently discontinue treatment due to COVID-19
- and who did not permanently discontinue study due to COVID-19

4.3.8. Analysis set with trial impact (disruption) due to COVID-19

The analysis set with trial impact (disruption) due to COVID-19 includes any patient:

- with any critical or major protocol deviation related to COVID-19

- or who permanently discontinued treatment due to COVID-19
- or who permanently discontinued study due to COVID-19

Critical or major protocol deviations related to COVID-19 will be reviewed and finalized before database lock.

4.4. Reporting Conventions

Statistical analysis will be performed using SAS® Version 9.4 or higher.

Standardized and validated SAS macros from PPD will be used to set-up table, listing, figure (TLF) formats (headers/footers and tabulation format) and tabulate the summaries. All tables and listings will be independently validated using double programming; all figures will be independently validated manually.

4.4.1. Treatment labels

The following treatment labels will be used in the Tables, Figures and Listings. Where applicable, in the listing,

- patients who are randomized but not treated will be presented in a “Randomized, not treated” column/by-line statement, which will be presented prior any other treatment group,
- patients who are not randomized but treated will be presented in a “Not randomized, treated” column/by line statement, which will be presented prior any other treatment group.

Table 4.4.1 Treatment labels

Treatment order	Treatment group	Treatment Label
1	Not randomized, treated	Not randomized, treated
2	Randomized, not treated	Randomized, not treated
3	Placebo	Placebo
4	Dupilumab 300 mg q2w	Dupilumab 300 mg q2w
5	Total	Total

